## **SUMMARY OF CHANGES**

## SYNOPSIS

Full Study Title	A Phase II Study of Pre-operative Endoscopic Botulinum Toxin Injection in the Prevention of Postoperative Pancreatic Fistula following Distal Pancreatectomy
Protocol #	22619
Coordinating Center	OHSU, Knight Cancer Institute
Clinical Phase	Phase II - Single Agent
Study Description	Pancreatic resections are inherently morbid operations with complication rates of approximately 40%, the most feared of which is leakage of pancreatic digestive enzymes into the abdominal cavity, termed postoperative pancreatic fistula (POPF). POPF occurs in approximately 30% of distal pancreatectomies, and can dramatically alter the recovery pathway. Pre-operative endoscopic botulinum toxin (BTX) injection into the Sphincter of Oddi has been hypothesized to reduce the rate of POPF following distal pancreatectomy. The present study is a single-arm Phase II interventional study investigating the use of endoscopic botulinum toxin injection into the Sphincter of Oddi prior to distal pancreatectomy to prevent POPF. Intervention will occur 7-14 days prior to planned distal pancreatectomy, and further data collection/treatment will occur per standard of care. Safety of the intervention will be assessed, and patients will be compared to matched historical patients for analysis of POPF rates.
Primary Objective	To determine the effect of pre-operative endoscopic BTX injection on clinically relevant POPF rates following distal pancreatectomy
Secondary Objectives	1) To determine the safety of pre-operative endoscopic BTX injection 2) To determine the effect of pre-operative endoscopic BTX injection on the rate of all POPF (biochemical and clinically relevant) following distal pancreatectomy
Exploratory Objectives	To evaluate differences in: 1) crPOPF, 2) POPF, 3) postoperative length of hospital stay, 4) rate of Clavien-Dindo grade III or greater complications, 5) rate of percutaneous drainage, 6) rate of unplanned re-operation, using a historical population matched for potential confounding clinicopathologic variables.
Primary Endpoint	Rate of clinically relevant POPF (crPOPF) in intervention group
Secondary Endpoints	1) Rate of serious adverse events following endoscopic BTX injection (e.g., clinical pancreatitis, bleeding, perforation, or other events delaying time to surgery or receipt of surgery) 2) Rate of any POPF in intervention group
Exploratory Endpoints	1) Clinically relevant POPF (binary) 2) Any POPF (binary)

	3) Postoperative Length of Hospital Stay (continuous) 4) Clavien-Dindo III or greater postoperative complications (binary) 5) Rate of percutaneous drainage procedure (binary) 6) Rate of unplanned re-operation (binary)
Key Inclusion Criteria	1. Patient scheduled for elective distal pancreatectomy or radical antegrade modular pancreatectosplenectomy (RAMPS), via open or laparoscopic technique 2. Participant aged $\geq$ 18 years 3. Ability to understand nature and individual consequences of clinical trial 4. Written informed consent 5. For participants of childbearing potential, a negative pregnancy test and adequate contraception until 14 days after trial intervention
Key Exclusion Criteria	1. Known hypersensitivity to any BTX preparation or to any of the components in the formulation 2. Infection at the proposed injection site, including cholangitis 3. Anatomy incompatible with planned intervention (e.g., Roux-en-Y gastric bypass, distal gastrectomy with Roux-en-Y or Billroth II reconstruction) 4. Acute pancreatitis within 2 weeks of planned study intervention 5. Pancreas divisum 6. ASA score $>$ III 7. Serious cardiovascular disease (e.g., Myocardial infarction in the past year, NYHA III/IV congestive heart failure, unstable angina). 8. Creatinine clearance $<$ 30mL/min 9. Liver cirrhosis (of any Child-Pugh grade) 10. Neuromuscular or any neurological disease with associated increased risk for a participant undergoing BTX injection 11. Prior BTX administration 12. Inability to obtain informed consent from participant or legally authorized representative. 13. Inability to comply with study and/or follow-up procedures 14. Pregnancy or lactation 15. Any condition that could result in undue risk for the participant and/or influence outcome measures (in the opinion of the investigator)
Number of Participants	Up to 64 participants will be consented. Up to 55 patients will undergo the study intervention such that 50 patients will undergo the study intervention and complete 30-day postoperative follow-up.

Duration of Therapy	A one-time endoscopic injection of BTX with no further study interventions
Duration of Follow Up	Up to 30 days following distal pancreatectomy.
Description of Study Intervention	
	Preoperative endoscopy with Sphincter of Oddi BTX injection will be the only trial-related intervention for patients participating in this trial. All the other procedures, including assessment of laboratory parameters, belong to the standard perioperative and postoperative procedures performed in patients undergoing distal pancreatectomy. In patients with childbearing potential, a pregnancy test will be performed during the routine preoperative laboratory examinations.
Statistical Analyses	This is a single arm, open-label, Phase II study to estimate the rate of clinically relevant POPF in participants that receive pre-operative endoscopic BTX injection. Using a Simon's 2-stage, a total of 50 evaluable participants will achieve an 88% power to detect a difference in crPOPF rate of 9.2% (H0: $\pi = 0.112$ versus Ha: $\pi = 0.02$ ; with a one-sided alpha level of 0.05). The trial will be continued following stage 1 if there is one or fewer crPOPF among the first 25 participants. If the study proceeds to stage 2, a total of 50 participants will be evaluated towards the primary endpoint, and the intervention considered promising if there are two or fewer cases of crPOPF.

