### 1.1.1 OVERVIEW OF STUDY TERMS

**Distal Pancreatectomy.** Distal pancreatectomy (removal of the distal pancreas +/- spleen) is indicated in nonmetastatic PDAC, and other neoplasms when disease is localized in the pancreatic tail, as well as in certain patients with chronic pancreatitis. A variant technique of distal pancreatectomy, termed radical antegrade modular pancreateosplenectomy (RAMPS) is often used specifically for malignancies of the pancreas. Pancreatic surgery is technically difficult and highly morbid, with POPF being the most feared complication by clinicians and patients.

**Postoperative Pancreatic Fistula (POPF).** POPF results when digestive enzymes normally secreted by the pancreas leak into the abdominal cavity following an operation, leading to a wide range of inflammatory and auto-digestive complications. POPF is defined by the International Study Group of Pancreatic Fistula (ISGPF) as an amylase level obtained from drainage fluid or abscess of greater than three times the upper limit of normal, starting from the third postoperative day (POD3). POPF is further classified by the ISGPF into biochemical leaks (asymptomatic elevations in amylase from surgical drain fluid that do not require additional treatment), Grade B POPF (requiring percutaneous or endoscopic drainage), or Grade C POPF (resulting in organ failure); together, Grades B/C constitute clinically-relevant POPF (crPOPF). Rates of POPF following distal pancreatectomy range from 20-50% with an average of 30%, with a 10-year average of at OHSU of 30.9% for all POPF and 11.3% for crPOPF.

[figure not shown]
**Sphincter of Oddi.** The Sphincter of Oddi is a smooth muscle valve located at the Ampulla of Vater that regulates the flow of bile and pancreatic secretions into the duodenum. Following distal pancreatectomy, the resting muscle tone of the Sphincter of Oddi may act as a dam, causing the “path of least resistance” for pancreatic secretions to be the cut edge of the pancreas, resulting in POPF as secretions exit into the abdominal cavity and cause an intense autodigestive and inflammatory reaction.

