## 11. STATISTICAL CONSIDERATIONS

### 11.1 STATISTICAL HYPOTHESIS

This study is a Phase II, open-label study to determine the effect of pre-operative endoscopic BTX injection on crPOPF rates following distal pancreatectomy. It is hypothesized that the rate of crPOPF in study participants will be significantly lower than the known historical rate of crPOPF.

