### 11.2 SAMPLE SIZE DETERMINATION

This will use a Simon's two-stage design. The two-stage design to test a difference of 9.2% (2% vs. 11.2%) has an expected sample size of 30.33 and a probability of early termination of 0.787. If the pre-operative BTX injection is effective, there is a 0.124 probability of concluding that it is not, equivalently 0.876 power. After the pre-operative BTX injection on 25 patients in the first stage, the trial will be terminated if 2 or more crPOPF. If the trial goes on to the second stage, a total of 50 participants will be studied. If the total number crPOPF is less than 3, the drug will be considered efficacious. Anticipating 10% drop-out (lost follow-up), up to 55 participants need to be enrolled to achieve 50 evaluable participants. The sample size and power analysis were conducted using PASS 15 software (<http://www.ncss.com/software/pass/>).

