#### 11.4.5 PLANNED INTERIM ANALYSES AND STOPPING RULE

A safety-run in to test the endoscopic BTX injection technique will be performed. During the safety run-in, the PI will evaluate patient safety outcomes including grade 3 or higher adverse events. Additionally, the study will be evaluated by the DSMC following the completion of the first three participant's safety evaluation periods (30 days following BTX injection or 30 days following surgery, whichever is longer). Progressive study enrollment will continue throughout the safety run-in, and enrollment will be halted if recommended by the DSMC after completion of the run-in. If 2 or more of the first 6 participants enrolled experience delay in planned surgery  $\geq$  14 days (due to significant GI hemorrhage, perforation, or adverse reaction to BTX) or pancreatitis requiring hospitalization, then the study will be halted for safety. If 2 or more of the first 6 participants experience delay in planned surgery  $\geq$  14 days (due to significant GI hemorrhage, perforation, or adverse reaction to BTX) or pancreatitis requiring hospitalization, the study will be halted for safety. An analysis of adverse events will be performed, and if an alteration in the intervention technique or other prophylactic treatment cannot be identified the study will be terminated. If an alteration or prophylactic treatment can be found, the study will resume with an additional 6 patient safety run-in with identical stopping rules.

A futility analysis will be conducted based on the stopping rule of Simon's two-stage design after 25 Stage I participants have met the eligibility criteria for the efficacy evaluable population (defined in 11.3.2). All participants enrolled on stage 1 (n=25) will need to complete the study intervention, distal pancreas resection, and 30 days of follow up for postoperative pancreatic fistula before the interim analysis can be completed. Recruitment will be paused until interim analysis is completed. The trial will be terminated if there are 2 or more crPOPF among these 25 participants. If there are less than 2 crCOPF among these Stage I participants, the trial will continue and enroll 25 additional participants in Stage II. The treatment will be considered promising and deserving of further investigation if there are less than 3 crCOPF among the total of evaluable 50 participants.

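### The stated two-stage rule has an exact one-sided type I error of 0.058, not the 0.05 given in the Synopsis

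*Combined protocol and SAP*

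**What the plan says.** The Statistical Analyses entry of the Synopsis sets a null crPOPF rate of 0.112 and an alternative of 0.02, and says that "a total of 50 evaluable participants will achieve an 88% power to detect a difference in crPOPF rate of 9.2" percentage points, "with a one-sided alpha level of 0.05". The trial continues past stage 1 with at most one crPOPF among 25 participants, and the intervention is promising with at most two among 50.

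Section 11.2 repeats the rates and the rule. It says the design "has an expected sample size of 30.33 and a probability of early termination of 0.787", and it gives a type II error of 0.124, "equivalently 0.876 power". It states no type I error. Section 11.4.5 applies the same counts and calls the treatment "promising and deserving of further investigation if there are less than 3 crCOPF" among 50 evaluable participants.

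Two other places bear on the point. Section 11.1 hypothesises that the crPOPF rate "will be significantly lower than the known historical rate of crPOPF". Section 1.1.1 gives the ten-year OHSU averages as "30.9% for all POPF and 11.3% for crPOPF", so the historical rate appears there as 11.3% and in the design as 11.2%.

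**The concern.** The null rate, stage sizes and cut-offs fix the type I error of a two-stage binomial design exactly. The plan supplies all of them, so the stated alpha can be checked, and it is the only alpha in the document. Discreteness usually leaves the attained error of such a design at or below the stated level. Here it lies above, which is the direction that favours the intervention.

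What is at stake is how a positive result is described. Read with Section 11.1, the Synopsis invites the reader to treat every promising result as significant at one-sided 0.05. If the trial ended with exactly two crPOPF in 50, that reading would be wrong, and whether the result counts as significant would be argued after the data were known.

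**Working it through.** **Inputs.** Null rate p0 = 0.112 and alternative p1 = 0.02 (Synopsis, Section 11.2). Stage 1: 25 participants, continue if 0 or 1 crPOPF. Final: 50 participants, promising if 2 or fewer in total (Synopsis, Sections 11.2 and 11.4.5).

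**Formula.** Let X be the stage 1 count and Y the stage 2 count, each Bin(25, p). Then

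P(promising | p) = P(X=0)·P(Y≤2) + P(X=1)·P(Y≤1).

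**Step 1: the plan's own figures.**

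- Early termination under the null: 1 − P(X≤1 | 0.112) = 1 − 0.21316 = 0.7868 (stated 0.787).
- Expected sample size under the null: 25 + 25 × 0.21316 = 30.33 (stated 30.33).
- Power at 0.02: 0.60346 × 0.98676 + 0.30789 × 0.91135 = 0.5955 + 0.2806 = 0.8761 (stated 0.876; 88% in the Synopsis).

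All three match, so these are the rates and cut-offs behind the design.

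**Step 2: type I error of the same rule.** At p = 0.112:

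0.05132 × 0.45810 + 0.16183 × 0.21316 = 0.0235 + 0.0345 = **0.0580**.

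The stated figure is 0.05.

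**Step 3: does another reading give 0.05?**

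| Reading | Type I error | Power at 2% |
|---|---|---|
| Stated rule, null 11.2% | 0.0580 | 0.876 |
| Stated rule, null 11.3% (Section 1.1.1) | 0.0557 | 0.876 |
| Interim look ignored, at most 2/50, null 11.2% | 0.0706 | 0.922 |
| Same stages and interim rule, final cut-off 1/50, null 11.2% | 0.0192 | 0.736 |

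The stated rule reaches 0.05 only at a null rate of 11.57%, which appears nowhere in the document. With these stages and this interim rule, the largest final cut-off that holds 0.05 is 1/50, and power there is 0.736.

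**Step 4: which results are affected.** The two-stage one-sided p-value is taken as the probability, at 11.2%, of passing stage 1 with a total no larger than observed:

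| Result | p-value |
|---|---|
| 0/50 | 0.0026 |
| 1/50 | 0.0192 |
| 2/50 | 0.0580 |

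Only 2/50 is promising without being significant at 0.05. Its probability is as follows.

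- At a true rate of 2%: 0.8761 − 0.7358 = 0.1403, which is 0.1403/0.8761 = 16% of all promising results.
- At a true rate of 11.2%: 0.0580 − 0.0192 = 0.0388, which is 0.0388/0.0580 = 67% of all false positives.

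**The case against.** The arithmetic is not open to dispute. The case on the other side is that it matters little.

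First, Section 11.4.1 plans no test, only the rate with a 95% exact confidence interval. The ordinary exact interval is 0.5% to 13.7% for 2/50, which includes 11.2%, and 0.05% to 10.6% for 1/50, which does not. The planned output would thus already separate the two results. This is true, but Section 11.4.1 does not say that the interval will be compared with 11.2%, and Section 11.1 does speak of a significantly lower rate. The interval would show the conflict without settling which statement governs.

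Second, the decision wording is a count rule for further study and not a claim of significance. That holds for the Synopsis and Section 11.4.5. Section 11.2 goes further and would call the drug efficacious.

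Third, the gap is small beside the uncertainty in the null. If the historical rate rests on the 353 resections mentioned in Section 4.4.1 (an assumption: 40/353 = 11.3%), its exact 95% interval is 8.2% to 15.1%, and the rule's type I error runs from about 0.18 to 0.011 across that range. This stands as a caution against reading 0.058 too finely. It does not make 0.05 the right figure for the null that the plan states.

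Fourth, setting the rule against a cut-off of 1/50 makes the design look further off than it is. With 25 in stage 1 and the same cut-offs, a total of 52 gives a type I error of 0.0496 and power of 0.870. That is fair: the shortfall amounts to about two participants.

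Finally, a sentence on significance in Section 11.4.1 goes beyond correcting a number. That is so, and the correction does not depend on it. It does follow from the p-values above and closes the ambiguity left by Section 11.1.

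**Conclusion.** The concern holds. At the stated null rate of 11.2%, the stated rule has a one-sided type I error of 0.058, so 88% power and an alpha of 0.05 are not delivered together. The excess is 0.8 percentage points. Nothing in the plan calls 0.05 nominal or gives the attained value.

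The consequence is confined to reporting. The count rule is the same wherever it appears, it remains a workable phase II screen, and no enrolment or stopping decision is affected. The one result at issue is exactly 2/50.

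The figures assume independent binomial outcomes, exactly 25 and 50 evaluable participants at the two analyses, and a null rate treated as known. The correction should be made, but it is not a reason to redesign the trial.

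**What to change.** - **Synopsis, Statistical Analyses:** replace the alpha of 0.05 with an attained one-sided alpha of 0.058.
- **Section 11.2:** add the attained one-sided alpha of 0.058 beside the power of 0.876, the early termination probability of 0.787 and the expected sample size of 30.33.
- **Section 11.4.1:** add a sentence such as: A result of 2/50 meets the promising rule but has a two-stage one-sided p-value of 0.058 against 11.2% and will not be reported as significantly lower at the 0.05 level; 1/50 gives p = 0.019.

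This costs one replaced figure, one added figure and one added sentence. It needs no extra participants and leaves the sample size, interim timing and cut-offs unchanged. The only price is a slightly less favourable stated alpha.

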## SCHEMATIC OF STUDY DESIGN

Procedure	BTX Injection		Surgery and Postoperative Period				
	Day 1	Day 7-14 (Pre-operative Medicine Appointment)*	Day 1 (Day of Surgery)	Day 4 (Postoperative Day 3)	Day of Discharge	Discharge + 7-14 Days (Post-Operative Follow-up)	Day 30
Physical exam	X		X*	X*	X*	X*	
Vital signs 	X	X*	X*	X*	X*	X*	
ECG (if indicated)		X*	X*				
Routine blood draw  (1 tablespoon)		X*	X*	X*			
Drain Fluid Analysis				X*			
Pregnancy test (if indicated)	X	X*	X*				
Review any adverse events		X	X				X
Review all other medications	X	X	X				
BTX Injection	X						
Distal Pancreas Resection			X*	X*			
IN THE EVENT OF OPERATIVE DELAYS, PATIENTS STILL EVALUABLE FOR EFFICACY IF RECEIVING SURGERY UP TO 28 DAYS FROM BTX INJECTION. A PRE-OPERATIVE MEDICINE APPOINTMENT PRIOR TO BTX INJECTION IS GENERALLY NOT NEEDED, BUT MAY BE REQUESTED FOR SOME PATIENTS DEPENDING ON HEALTH STATUS AND CLINICIAN DISCRETION							

\* Interventions/monitoring per standard of care

 Can include heart rate, blood pressure, height, weight, oxygen saturation, temperature

 Can include CBC with differential, chemistry, magnesium, uric acid

## LIST OF ABBREVIATIONS

AE	Adverse event
ASA	American Society of Anesthesiologists
BTX	Botulinum Toxin
BUN	Blood urea nitrogen
CBC	Complete blood cell (count)
CFR	United States Code of Federal Regulations
CONSORT	Consolidated Standards of Reporting Trials
CRC	Clinical Research Coordinator
CRMS	Clinical research management system
crPOPF	Clinically-relevant postoperative pancreatic fistula
CRQA	Clinical Research Quality & Administration
CRRC	Clinical Research Review Committee (OHSU)
CTCAE	Common Terminology Criteria for Adverse Events
CTMS	Clinical Trial Management System
DSMB	Data and Safety Monitoring Board
DSMC	Data and Safety Monitoring Committee
DSMP	Data and Safety Monitoring Plan
ECG, EKG	Electrocardiogram
ECOG	Eastern Cooperative Oncology Group
eCRF	Electronic Case Report Form
eCRIS	Electronic Clinical Research Information System
EDC	Electronic data capture
FDA	United States Food and Drug Administration
HGB	Hemoglobin
HIPPA	Health Insurance Portability and Accountability Act
ICF	Informed Consent Form
IND	Investigational new drug application
IRB	Institutional Review Board
ISGPF	International Study Group of Pancreatic Fistula
IV	Intravenous
LFT	Liver function test
MedDRA	Medical Dictionary for Regulatory Activities
N/A	Not applicable
NYHA	New York Heart Association
NSQIP	National Surgical Quality Improvement Project
OHSU	Oregon Health & Science University
PDAC	Pancreatic Ductal Adenocarcinoma
PI	Principal Investigator
PO	Per os (by mouth, orally)
POPF	Postoperative pancreatic fistula
RAMPS	Radical antegrade modular pancreateosplenectomy
SAE	Serious adverse event
SGOT	Serum glutamic oxaloacetic transaminase
SGPT	Serum glutamic pyruvic transaminase
SNAP	Soluble N-ethylmaleimide sensitive fusion protein
SNARE	Soluble N-ethylmaleimide sensitive fusion protein receptors
TSMP	Trial Specific Monitoring Plan
ULN	Upper limit of normal
UP	Unanticipated Problem
WBC	White blood cell (count)

## 1. BACKGROUND INFORMATION AND SCIENTIFIC RATIONALE

### 1.1 BACKGROUND

Over 50,000 new cases of pancreatic cancer are diagnosed in the United States each year, with 96% being pancreatic ductal adenocarcinoma (PDAC). PDAC carries a dismal prognosis with an overall 5-year survival of 7.2%, however patients with resected disease can achieve 5-year survival rates of up to 30%. Pancreatic resections are inherently morbid operations with complication rates of approximately 40%; one of the most feared complications by clinicians and patients is leak of pancreatic digestive enzymes from the cut pancreas into the abdominal cavity, termed a postoperative pancreatic fistula (POPF).

POPF occurs in approximately 13% of pancreaticoduodenectomies and up to 30% of distal pancreatectomies, and can dramatically alter the recovery pathway. In pancreatic cancer, major postoperative complications (including POPF) are associated with non-receipt and delays to adjuvant chemotherapy, significantly reducing long-term survival following a curative-intent resection. Interventions to reduce the rate of POPF therefore have the potentially to dramatically improve both short and long-term outcomes in patients undergoing distal pancreatectomy.

One proposed mechanism for POPF following distal pancreatectomy is that the Sphincter of Oddi, which normally regulates the flow of pancreatic secretions into the intestine, continues to serve as a barrier and acts like a dam, promoting pancreatic fluid exit from the cut edge of the pancreas, causing a POPF. Pre-operative endoscopic injection of botulinum toxin (BTX) into the Sphincter of Oddi has been suggested to lower the rate of POPF after distal pancreatectomy, as paralyzing the muscle theoretically removes this resistance and would promote normal flow of pancreatic fluids into the duodenum until healing is complete. These results have not been uniformly reproduced, with one study performing BTX injection at a median of 1 day pre-operative not demonstrating a difference in POPF rates, possibly due to the delayed onset of BTX efficacy. Additionally, this intervention has never been studied in an American population, though a randomized trial is accruing patients in Europe. Of note, endoscopic BTX injection into the Sphincter of Oddi has previously been shown to be efficacious for abdominal pain resulting from Sphincter of Oddi dysfunction and post-cholecystectomy biliary pain, suggesting that the paralysis afforded by BTX can be therapeutic.

Endoscopic BTX administration is an innovative method to reduce POPF, as previously investigated strategies for POPF prevention have primarily been either intraoperative (such as absorbable mesh placement) or postoperative medication-based interventions (such as pasireotide or hydrocortisone). Additionally, while external pancreatic duct stenting has shown efficacy in preventing POPF in patients undergoing pancreaticoduodenectomy, prophylactic endoscopic stenting and sphincterotomy has not been well-studied in the prevention of POPF following distal pancreatectomy, though prospective trials are accruing (NCT03314337). Importantly, sphincterotomy and instrumentation of the pancreatic duct during stent placement imparts a higher risk of acute pancreatitis than BTX administration, which does not instrument the duct itself.

In short, the present study represents a novel application of an established technique, and may have a significant positive impact on clinical practice by improving the perioperative care and outcomes of patients undergoing distal pancreatectomy. In the case of pancreatic cancer, a reduction of POPF rates may translate to higher receipt and fewer delays to adjuvant chemotherapy and improved survival.

